## 7.6 Follow-up of AEs and SAEs

All AEs and SAEs documented at a previous visit/contact and are designated as ongoing, will be reviewed at subsequent visits/contacts.

All AEs and SAEs will be followed until resolution, until the condition stabilises, until the event is otherwise explained, or until the Participant is lost to follow-up. Once resolved, the appropriate AE/SAE CRF page(s) will be updated.

## 7.7 Risk Management Process

Table 1 below details the Risk Identification, Evaluation and Management plan for this study.

It will ensure that risk and uncertainty are appropriately managed for the duration of the study. The risk management process is in accordance with the NHMRC National Statement on Ethical Conduct in Research Involving Humans (2007).

**Table 1: Risk Analysis Matrix**

**Consequence**

Likelihood	Negligible	Minor	Moderate	Major	Extreme
Almost Certain					
Likely					
Possible					
Unlikely					
Rare					

**Response To Risk**

	Very High	Immediate action required
	High	Urgent attention or investigation required
	Medium	Require specific attention
	Low	Manage through routine procedures

**Risk Identification, Evaluation and Management Plan**

	Risk	Description	Possible Effects			Risk Management strategies
			Likelihood	Consequence	Rating	
1.	Psychological discomfort during assessments	Participants in the clinical groups may experience psychological discomfort when answering questions in the clinical interview and cognitive assessments.	Possible	Minor-moderate	Medium	The PICF clearly states the potential risk of discomfort.  Recruitment of experienced mental health clinicians who will be able to minimise and manage discomfort.

						
Participants in the clinical groups will be clinically assessed at baseline, end of treatment and 3 months post treatment.
 
Participants are given the opportunity to discuss any concerns/discomforts re previous appointment.
 
Clinicians will direct and assist participants to gain support if required.

2.	Psychological discomfort with self-disclosure in a session	Participants in the clinical groups may experience discomfort in self –disclosure during sessions.	Possible	Minor-moderate	Medium	
The PICF clearly states the potential risk of discomfort.
 
Recruitment of experienced mental health clinicians who will be able to minimise and manage discomfort.

						Clinicians will direct and assist participants to gain support if required.
3.	Inconvenience of participating in the trial	Participants may be inconvenienced by time taken to participate in the trial.	Possible	Negligible	Low	
The PICF for the clinical groups clearly states the battery of clinical assessments to be completed and the approximate time and frequency for clinical assessment visits.
 
Participants will be given as many breaks as necessary throughout the clinical assessment visit.
 
.
 
Participants will be reminded that the trial is voluntary, and they can withdraw at any time.

4.	History of self-harm/suicidal ideation	Participant expresses suicidal ideation.	Possible	Moderate-severe	High	Recruitment of experienced mental health clinicians who are trained in conducting risk

						
assessment and managing high risk situations.
 
Research staff will have access to a clinically trained senior staff including a Project Manager and Chief Investigator who will assist research staff to conduct risk assessment and implement risk management plan if required i.e. notifying treating team and assisting in the participant accessing appropriate support (e.g. emergency services)
 
Previously identified high risk patients and recent risk assessments will be discussed at weekly team meetings and their management reviewed by senior research staff (including Project Manager and Chief Investigator).

--	--	--	--	--	--	---

						
Research staff will be given support and feedback on risk assessments and their management to improve skills throughout the project.

5.	
Transporting participants in QLD Health work vehicles
	
Research staff will be transporting participants to pathology appointments and may be required to transport participants to the interview site.
 
There may be risk associated with motor vehicle accident
 
There may be risks associated with unpredictable behaviour of a patient whilst being transported.
	Possible	Minor-Moderate	Medium -High	
Research staff will have a current QLD Driver’s Licence and completed the mandatory Driver Safety E-Learning Course.
 
Recruitment of experienced mental health clinicians who will be able to and manage unpredictable behaviour.
 
Research staff will carry a mobile phone and adhere to a sign in/out policy and advise the Project Manager of the address they will be attending.

6.	Psychological discomfort during MRI	Participants may become distressed (for example as a result of feeling claustrophobic) within the MRI.	Possible	Minor – Moderate	Medium-High	
Screening – advised and asked if this is likely.
 
Discussed again at the time of screening. Also advised MRI can be ended if this occurs. Advised of emergency button to press in this instance.
 
Checked on during the MRI by radiographer using intercom system. The participant is then able to advise if they are becoming distressed.

7.	Risk of physical harm during MRI	If a participant undergoes an MRI with metal in their body this can result in physical harm to the participant (i.e. the implant may cease to	Possible	Major	High	A strict metals check procedure will be followed to mitigate the risk of scanning a participant with metal in their body. Three metal checks will occur;

		
function, in the case of pacemaker, brain clip, aortic clip or neurostimulator).
			
Firstly, by a member of the research team at the time of recruitment and screening.
 
The second by trained scientist, during the session and prior to the MRI scan.
 
The third by the radiographer who will conduct the MRI scan, immediately prior to the MRI scan.
 
The metal check will be documented using CAI developed metal checklist. If a participant responds yes to any of the screening questions, these will be investigated (e.g. by Xray, review of medical notes etc) to assess suitability for scanning.
 
They will not be scanned unless the radiographer is confident the participant does not have metal

--	--	---	--	--	---

						within them that could result in harm during the MRI scan.
8.	An abnormality found in the MRI scan	Becoming aware of neurological abnormalities of a participant as a result of the MRI.	Rare	Minor-Moderate	Low	
The Participant Information Sheet outlines the process that will be followed if abnormalities are found. The information sheet advises participants they will be notified of any abnormality identified and that knowledge of that may have consequences (e.g. ability to work in certain professions, obtain life or health insurance). With reference to this, the information sheet states, “If you do not want to know, then it is better not to participate.”
 
Action to be taken: Pass information to [name], she will determine most appropriate action to be taken,

						which may include contacting treating clinician.
--	--	--	--	--	--	--

## **8. Participant Completion**

Participants are considered to have completed the study if they complete 20 sessions (equivalent to 20 hours of the program) (intervention group only) and completion of post-intervention / end assessment measures (clinical groups). The healthy control group will only be required to complete the fMRI task.

### **8.1 Participant Withdrawal by the Investigator**

Worsening of mental state such that the patient is admitted to hospital or their ability to provide ongoing informed consent is compromised.

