## **7. Adverse Events (AE) and Serious Adverse Events (SAE)**

All adverse events reported between consent and final follow-up will be recorded. The investigator or designee will ask the Participant non-leading questions to detect adverse events e.g. “How have you been over the last 5 weeks”. We expect that adverse events will occur during the study related to fluctuations in the underlying mental disorder and medications. The investigator is responsible for the detection and documentation of events meeting the criteria and definition of an adverse event (AE) or a serious adverse event (SAE) as provided in this protocol. During the study, when there is a safety evaluation, the investigator or site staff will be responsible for detecting AEs and SAEs, as detailed in this section of the protocol

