### **7.1 Definition of a Serious Adverse Event (SAE)**

A serious adverse event is any untoward medical occurrence that, at any dose:

- a) results in death
- b) is life threatening
- c) requires hospitalisation or prolongation of an existing hospitalisation.
- d) results in disability/incapacity, or
- f) Any event deemed by the investigator as being a significant medical event.

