## 7.2 Time Period, Frequency, and Method of Detecting AEs and SAEs

All adverse events will be recorded between the time of consent and the follow-up visit. Each Participant will be monitored regularly by the investigator and study personnel for adverse events occurring throughout the study. The research team will enquire about AEs by asking the following non-leading questions:

At the first scheduled visit (baseline) participants will be asked:

*“How are you feeling?” Does your current treatment cause you regular side effects? Do you have any general health conditions that cause you problems on a regular basis (e.g. that we might expect to occur over the duration of this study?)”*

At subsequent scheduled visits, participants will be asked:

*“Since your last visit, have you had any health problems?”*

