## 7.3 Recording of AEs and SAEs

If an AE/SAE occurs, the investigator will review all documentation (e.g. hospital progress notes, laboratory, and diagnostic reports) relative to the event. We will then record all relevant information regarding an AE/SAE in to the CRF, and code the AE according to industry standard MEDDRA coding rules.

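### Section 8.1 withdraws patients on psychiatric admission without separating stopping study procedures from leaving the study, so end data are lost because of an outcome-related event

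*Protocol*

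**What the plan says.** The whole of Protocol section 8.1 (Participant Withdrawal by the Investigator) is one line: "Worsening of mental state such that the patient is admitted to hospital or their ability to provide ongoing informed consent is compromised". The two grounds are joined by an alternative, so an admission for worsening mental state counts whether or not capacity is affected. No duration, exception or route back is given. Nothing is said about safety contact or an end assessment afterwards.

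Five other parts of the protocol bear on the same patient:

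- Section 7.1(c) counts as serious any event that "requires hospitalisation or prolongation of an existing hospitalisation".
- Section 7.6 states: "All AEs and SAEs will be followed until resolution, until the condition stabilises". It goes on to two further end points, another explanation and loss to follow-up. Events already documented "and are designated as ongoing, will be reviewed at subsequent visits/contacts".
- Section 3.2.1 offers TAU to a CR participant whose changed circumstances prevent completion of CR. It re-allocates to TAU anyone who chose CR but did not complete more than 5 sessions. The TAU group completes the pre and post measures.
- Section 8 makes the end measures a condition of completion in the clinical groups.
- Section 9.2 analyses each outcome by a 3 (group) x 2 (baseline, post-intervention) mixed ANOVA.

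**The concern.** The trigger for withdrawal is itself a clinical outcome. A patient admitted because mental state has worsened is likely to score worse on symptoms, functioning and perhaps reward learning at the end assessment. If such patients leave before that assessment, the pre-post change is measured among those who stayed well enough to remain. The CR-TAU contrast is distorted when the two patient groups lose different shares of patients in this way. That is plausible here because allocation follows patient preference and is not randomised.

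The situation is foreseeable on the protocol's own account. Section 7 says: "We expect that adverse events will occur during the study related to fluctuations in the underlying mental disorder and medications". A missing-data method in an analysis plan can model values that were not collected, but it cannot restore them.

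**Working it through.** The protocol states no admission rate, dropout rate, power or alpha, so there is no figure of its own to reproduce. The check is first textual, then an illustration on assumed inputs.

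**Step 1: follow one patient through the text.** Take a CR participant admitted for worsening mental state after at most 5 sessions and discharged soon after with capacity.

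| Section | Consequence for this patient |
|---|---|
| 8.1 | Withdrawn by the investigator |
| 3.2.1 | Re-allocated to TAU, which has pre and post measures |
| 7.1(c) and 7.6 | The admission is an SAE, followed until one of the listed end points |
| 8 | Not a completer without the end measures |
| 9.2 | Baseline value present; no post value if 8.1 is applied as leaving the study |

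Sections 8.1 and 3.2.1 give this patient different dispositions. After more than 5 sessions the overlap is less certain: it depends on whether an admission counts as changed circumstances, which the text leaves open.

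**Step 2: effect on the group means.** Let p be the proportion of a group admitted before the end assessment, and d the amount, in SDs of change, by which admitted patients do worse than the rest. If the remaining patients have mean change m:

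- Mean of the whole group = (1 - p) x m + p x (m - d) = m - p x d.
- Mean of those assessed = m, so it is overstated by p x d.
- Shift in the contrast = d x (difference between the two groups' p).

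Assume d = 1 SD, with 5% admitted in one group and 20% in the other. That is 20 x 0.05 = 1 and 20 x 0.20 = 4 patients. The shift is 1 x (0.20 - 0.05) = 0.15 SD. If TAU has the higher rate, the advantage of CR is understated; if CR has it, the advantage is overstated. With equal rates the contrast shifts by 0, although each group's own change is still overstated by p x d.

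**Step 3: the same question under a second model.** Let change scores be normal and let the fraction q with the worst values of an admission propensity leave, where that propensity has correlation rho with change. With z_q the q-quantile and phi the density of the standard normal, the assessed mean rises by rho x phi(z_q) / (1 - q):

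| Lost from 20 | q | rho = 0.3 | rho = 0.5 | rho = 1 |
|---|---|---|---|---|
| 1 | 5% | 0.03 SD | 0.05 SD | 0.11 SD |
| 2 | 10% | 0.06 SD | 0.10 SD | 0.20 SD |
| 4 | 20% | 0.11 SD | 0.18 SD | 0.35 SD |

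These are shifts within one group. The contrast moves by the difference between the two groups' shifts.

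**Step 4: how often the rule would apply.** At assumed admission rates of 5%, 10% and 20% among the 40 patients, 2, 4 and 8 admissions are expected. The chance of at least one is 1 - 0.95^40 = 0.87, 1 - 0.90^40 = 0.985, and close to 1.

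**The case against.** A reader might infer that withdrawal ends safety follow-up, so that a site cannot obey both 8.1 and 7.6 and the outcome of the SAE is lost. The text does not support this. Section 7.6 allows review at contacts as well as visits, and withdrawal is not among its end points. Section 7.3 says that "the investigator will review all documentation (e.g. hospital progress notes, laboratory, and diagnostic reports) relative to the event", which needs no study visit. Section 6 states that all clinical patients are registered with the service and that the study team liaises with its staff. The duty therefore continues; what 8.1 lacks is a statement that it does.

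Nor would the rule hide a harm of CR, or a benefit in preventing relapse, from the record. Section 7.2 provides: "All adverse events will be recorded between the time of consent and the follow-up visit". Admissions are graded for intensity and causality under 7.4 and 7.5, and withdrawals are counted in the screening log of 9.2.1. Only the end scale scores and imaging are at risk.

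It can fairly be said that 8.1 is a fragment that does not forbid an end assessment after discharge. That is correct, but the protocol nowhere provides for one. The Protocol Compliance paragraph in section 12 makes participants handled contrary to the protocol ineligible for analysis, so a site's own initiative is a weak safeguard.

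The sizes are also modest and rest on assumptions. With 20 per group, the standard error of a contrast in SD units is about the square root of 2/20 = 0.32, so 0.15 SD is under half a standard error, and section 9.1 calls this a pilot and not an effectiveness study. This limits the weight of the point but does not remove it, since the bias is avoidable at little cost.

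**Conclusion.** The point holds as one about outcome-related loss of end data and an unclear withdrawal rule, not as one about lost safety follow-up. Read as written, 8.1 removes patients from the end assessment because of an admission, even where capacity is retained or regained. It also fits poorly with the re-allocation rule in 3.2.1.

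The size cannot be fixed from the documents. A 0.15 SD shift in the CR-TAU contrast requires both the assumed 5% v 20% difference in admissions and the assumed 1 SD worse change; equal rates give 0. The effect concerns only admissions before the end assessment. The second ground in 8.1, compromised ability to consent, is a legitimate limit on research assessments and is not part of the criticism. The change is worth making because it is inexpensive and uncollected data cannot be recovered later.

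**What to change.** Reconcile section 8.1 with sections 3.2.1, 7.1(c) and 7.6:

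- Separate stopping study procedures from leaving the study, and say which of the two an admission leads to.
- State how 8.1 and the re-allocation rule in 3.2.1 apply to a CR participant who is admitted, so that each such patient has one disposition.
- State that SAE follow-up under 7.6 continues after either step, through contacts and hospital records.
- Provide that the end assessment is sought from admitted patients where consent and capacity allow, using the process in 3.6.1, and that data already collected are kept.

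The clinical criteria for stopping CR, scanning or participation should stay with the investigator and treating team; no replacement threshold is proposed here.

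The cost is a protocol amendment with ethics approval. The Version Control paragraph classes a change of content as significant, so it needs a full version step. Some end assessments will be late, with added variation in timing and some effort to re-confirm capacity and rebook scans.

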## **9. Data and analysis**

### **9.1 Sample Size and Power**

This is a pilot study to assess possible mechanism of effect of CR and the fMRI task in examining neural pathways involved in motivation not an effectiveness study.

### **9.2 Statistical Analysis**

Participants' medication dosages will be converted to olanzapine equivalents using Leucht et al. (2016) guidelines. Outcome measures will be analysed using the SPSS Version 27 software package. A series of 3 (group: intervention, patient control; healthy control) x 2 (time: baseline, post-intervention) mixed factorial ANOVAs will be conducted to evaluate the treatment group differences for each of the outcome measures. If the normality assumption is violated, non-parametric analyses will be conducted.

Standard pre-processing of the functionally weighted images is carried out using SPM12 (<http://www.fil.ion.ucl.ac.uk/spm/software/spm8>, 2013; Friston, 2003). The pre-processing steps follows: slice timing on the functional images, to correct for differences in slice acquisition times within each volume using the middle slice as reference; realignment (estimate and reslice) on the functional images, to correct for inter-scan movement within each run (defined as >3 mm translation, >2 degrees rotation); co-registration of the functional and structural images; segmentation of the structural image, with heavy regularisation (0.1) recommended for MP2-RAGE sequence; normalization of the resliced images into a standardized, stereotaxic space (according to the Montreal Neurological Institute template); and smoothing of normalized images with a 8mm full-width-at-half-maximum isotropic Gaussian kernel.

We will adopt the General Linear Model approach for event-related designs will be conducted using SPM8 (<http://www.fil.ion.ucl.ac.uk>). For the first-level analysis task-related changes in blood-

oxygen-level dependent (BOLD) signal will be estimated at each voxel, for each participant. Head motion parameters will be included as a regressor to account for participant motion during the course of the experiment. A 1/128 Hz high-pass filter will be used to remove slow signal drifts, and a canonical hemodynamic response function with no derivatives will be selected. Computational Modelling ([https://en.wikipedia.org/wiki/Computational\\_model](https://en.wikipedia.org/wiki/Computational_model)) will allow the estimation of learning parameters at each point in time, during each task condition, for each participant. We will employ a Variational Bayesian framework to compute how the value of each button was estimated based on the behavioural choices made, and feedback received. This allows us to measure how learning occurred during the experimental task and the subprocesses which must underlie this learning. This provides an accurate way to calculate each participants learning rate, and learning competency, based on the computation necessary to perform the task. These learning parameters will be the primary focus of first level fMRI modelling, allowing investigation of the neural systems which carry out each learning subprocess. Second level group analyses will examine how learning in patients differed from that observed in control participants, and how Cognitive Remediation therapy altered learning efficiency and the underlying neural activity. We will correct for multiple comparisons, voxel-level threshold will be set at  $p < 0.05$  family-wise error corrected.

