Social environments are dynamic with constant rapid changes, hence social situations require a rapid behavioural adjustment in response to ever-changing social feedback. People with schizophrenia have impaired social functioning and recent studies have shown that they also have impaired social reward processing (Catalano, Heerey, & Gold, 2018; Robberegt & Fett, 2017). Social approval induces rewarding feelings and is associated with increased activation in regions and networks associated with reward (Izuma, Saito, & Sadato, 2008; L. Rademacher et al., 2010; Spreckelmeyer et al., 2009). In those with schizophrenia there is reduced activity in common reward brain regions during the experience of social reward (Lee & Reavis, 2017), suggesting that they may have a reduced experience of the rewarding feeling of positive social attention. Positive social interactions have benefits for mental well-being and give life a sense of meaning (Uchino, Cacioppo, & KiecoltGlaser, 1996). In particular receiving praise and attention from others improves self-esteem (Hill, 1987) and increases motivation (Leary, 2007). Although social reward has major impacts on functional outcome, only recent efforts have explored social reward processing in schizophrenia.

Further behavioural evidence suggests that the RL difficulties to be more pronounced in learning from positive rather than negative feedback (Gold et al., 2008). This provides a further link between the effects of impaired RL and negative symptoms as learning preferentially from negative outcomes is likely to lead to behavioural avoidance, social withdrawal and have a negative impact on motivation. This hypothesis is supported by recent research suggesting that the magnitude of RL impairment, particularly for positive feedback, is associated with negative symptoms severity (Gold et al., 2012).

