### **3.2 Study Population**

#### **3.2.1 Intervention and treatment as usual patient groups**

Participants (n=40) with a diagnosis of a schizophrenia spectrum disorder, based on current medical records will be recruited from the teams of the Metro South Addiction and Mental Health service (MSAMHS). Participants (n=20) that are not interested in completing CR will form the patient TAU control group and will complete the pre and post measures only. Thus, group intervention allocation selection will be based on individuals' preference to participate in CR. If a participant initially signs up to the intervention group but due to change in circumstances is unable to complete CR, they will be offered the opportunity to become part of the TAU group. Individuals that initially choose to complete CR therapy but then fail to complete more than 5 sessions will be re-allocated to the control (treatment as usual) group.

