### **3.3 Number of participants**

Forty individuals with a diagnosis of schizophrenia spectrum disorder and 20 healthy individuals without a diagnosis of schizophrenia spectrum disorder. Total N is 60 participants.

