### **3.6 Participant Information and Informed Consent**

A member of the research team will conduct the consent process. As part of the consent process the potential participant will be given the Patient Information and consent sheet. The information will also be read to the person and any questions answered by the research team member. The potential participant will be allowed as much time as they require to consent. During the consenting process, all participants will be informed that they have the right to withdraw consent from the study at any time without prejudice and withdrawal from the study will not affect their current or future care.

Revocation of consent forms will be completed for those participants who choose to withdraw from the study.

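### The two-visit ANOVA in section 9.2 discards the baseline of any patient without an end assessment; if dropout follows baseline learning, its patient-versus-healthy contrast is understated, and the CR-versus-TAU change is biased only if dropout differs between arms

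*Protocol*

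**What the plan says.** Section 9.2 names both the model and the software for the outcome measures: "A series of 3 (group: intervention, patient control; healthy control) x 2 (time: baseline, post-intervention) mixed factorial ANOVAs will be conducted", and "Outcome measures will be analysed using the SPSS Version 27 software package". The only alternative is for non-normal data: "If the normality assumption is violated, non-parametric analyses will be conducted". The protocol names no mixed model, no imputation and no baseline-only comparison of the outcome measures.

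The sample is small: "Forty individuals with a diagnosis of schizophrenia spectrum disorder and 20 healthy individuals without a diagnosis of schizophrenia spectrum disorder", with 20 patients intended for each clinical arm. Section 9.1 gives no dropout allowance and describes the purpose thus: "This is a pilot study to assess possible mechanism of effect of CR and the fMRI task in examining neural pathways involved in motivation".

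Withdrawal is foreseen. Section 3.6 states: "Revocation of consent forms will be completed for those participants who choose to withdraw from the study". Section 8.1 withdraws patients who deteriorate to the point of admission or of doubtful capacity to consent, and section 9.2.1 plans a log that counts withdrawals.

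The introduction cites research that "the magnitude of RL impairment, particularly for positive feedback, is associated with negative symptoms severity", and it connects impaired reward processing with motivational deficits. In section 3.2.1, "group intervention allocation selection will be based on individuals' preference to participate in CR". The same section moves early CR non-completers to TAU.

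**The concern.** The classical two-visit mixed ANOVA works on complete pairs. A patient with a baseline and no end value contributes to neither the group effect nor the group-by-time effect.

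This matters if those who leave differ at baseline from those who stay. The protocol's own account of the illness makes that plausible: a worse reward-learning deficit goes with more severe negative symptoms and poorer motivation, and a poorly motivated patient is more likely to miss a second assessment. Two contrasts are exposed:

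- **Patients versus healthy controls.** The retained patients would look less impaired than the enrolled patients, so the deficit would be understated.
- **CR versus TAU change.** If one arm loses more of its impaired patients, the remaining arms differ at baseline. Regression to the mean then enters the difference in change.

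The baseline values that would repair the first contrast, and under missingness at random the second, will already have been collected.

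**Working it through.** The protocol has no dropout or power figure to reproduce. The check therefore asks how large the effect would be under stated assumptions.

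**Inputs**
- From the protocol: 20 patients per clinical arm (sections 3.1 and 3.2.1). A CR effect of 0.45 SD (introduction) serves only as a yardstick, because it refers to global cognition and not to reward learning.
- Assumed: missing end visits in CR/TAU of 20%/5% or 30%/10%; correlation λ of the dropout tendency with baseline learning of 0.3 or 0.5; pre-post correlation r of 0.5, 0.6 or 0.7; SD 1 at both visits; higher scores mean better learning.

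**Step 1: shift of the retained baseline mean.** If an arm loses the fraction d with the lowest dropout tendency, the shift is λ × φ(z_d)/(1 − d), where z_d is the normal quantile at d. The factor φ(z_d)/(1 − d) is 0.109 at 5%, 0.195 at 10%, 0.350 at 20% and 0.497 at 30%.

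| Dropout CR/TAU | λ | Shift CR | Shift TAU | Mean shift |
|---|---|---|---|---|
| 20%/5% | 0.3 | 0.105 | 0.033 | 0.069 |
| 20%/5% | 0.5 | 0.175 | 0.054 | 0.115 |
| 30%/10% | 0.3 | 0.149 | 0.058 | 0.104 |
| 30%/10% | 0.5 | 0.248 | 0.097 | 0.173 |

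The mean shift is the understatement of the baseline deficit: 0.07 to 0.17 SD. The ANOVA's group main effect averages the two visits and moves by (1 + r)/2 of this, that is 0.75 to 0.85 of it.

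**Step 2: bias in the CR-minus-TAU change.** Expected change among the retained moves by (r − 1) × shift in each arm, so the bias is (r − 1) × (shift in CR − shift in TAU).
- 30%/10%, λ = 0.5, r = 0.6: (0.6 − 1) × (0.248 − 0.097) = −0.060 SD.
- Smallest (20%/5%, λ = 0.3, r = 0.7): −0.3 × 0.072 = −0.022 SD, or 5% of 0.45.
- Largest (30%/10%, λ = 0.5, r = 0.5): −0.5 × 0.151 = −0.075 SD, or 17% of 0.45.
- Equal dropout with equal λ: the shifts cancel and the bias is zero.
- Percentages exchanged between the arms: same size, opposite sign.

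**Step 3: set against precision.** In a simulation of the same scenarios (8,000 runs each), standard errors were 0.26 to 0.37 for both estimators. In the example they were 0.313 for complete cases and 0.322 for the likelihood estimate, so the bias is 0.060/0.313 = 0.19 standard errors. The likelihood estimate had bias of at most 0.005 SD. Total root mean squared error hardly changed.

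**Step 4: a different dropout model.** Here dropout is logistic in the baseline score (log-odds slope −0.7 to −1.5 per SD), with an assumed true deficit of −0.80 SD and a true change of 0.45.
- Deficit among completers: −0.73 to −0.68 at 10% dropout, −0.67 to −0.57 at 20%, −0.61 to −0.47 at 30%. It stays at −0.80 if dropout is unrelated to baseline.
- Change at 30%/10%: 0.39 to 0.35 (r = 0.5) or 0.41 to 0.39 (r = 0.7).
- Change with equal dropout: about 0.45 throughout.
- Using all baselines returned 0.446 to 0.454 in every scenario.

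Steeper dependence therefore gives larger figures than step 1, but the pattern is the same.

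**The case against.** **Handling of missing values belongs in a statistical analysis plan.** The protocol never says that incomplete cases are dropped, and an ANOVA can be run on imputed data. That is fair as to wording: listwise deletion is a property of the named method and its usual SPSS procedure, not a sentence in the protocol. The estimator itself is fixed in section 9.2, however, so asking for a better one does not ask for missing detail.

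**Hypotheses 1A and 2A may not rest on this ANOVA.** A reader might infer that the trial's test of the deficit is bound to be understated. The documents do not support that. Section 9.2 also plans second-level group analyses of patients and controls, which could use every baseline scan; their time points are not stated. The quoted ANOVA has no social/non-social factor, so as written it cannot test hypothesis 2A. The understatement applies to the ANOVA's own contrast.

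**Dropout need not be heavier in CR.** A reader might infer that twice-weekly sessions make CR lose more patients and that the bias runs against CR. Section 3.2.1 moves early CR non-completers to TAU, which could shrink or reverse the imbalance. Preference allocation may also place less motivated patients in TAU from the start. The sign is open.

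**The link from deficit to dropout is an inference.** The introduction speaks of symptoms and motivation, not of study attrition. It is plausible, not documented.

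**The mixed model has its own assumption.** Withdrawal for worsening during the study (section 8.1) may not be at random, and the model does not correct that. Nor is missingness at random simply the weaker assumption: if dropout follows a stable trait, the complete-case change can be unbiased.

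**The bias in change is small** beside its standard error and, possibly, beside selection from non-random allocation, which this remedy leaves untouched. That stands.

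**Conclusion.** The point holds in a limited form. The ANOVA as fixed uses only patients with both visits and throws away baseline values already collected.

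The firmer part is the patient-versus-healthy contrast within that ANOVA. It is understated whenever dropout depends on baseline learning, by about 0.07 to 0.17 SD under the assumptions of step 1 and by more if the dependence is steeper. Using all baselines repairs this without any assumption about why later visits are missing.

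The weaker part is the CR-versus-TAU change. Bias needs dropout, or its dependence on baseline, to differ between arms. It is then about 0.02 to 0.08 SD under 20%/5% or 30%/10%, zero if the arms are alike, and of uncertain sign.

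All dropout inputs are assumed. The gain is in bias; no gain in power is claimed.

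**What to change.** In section 9.2:

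1. For CR versus TAU, replace the ANOVA with a linear mixed model (SPSS MIXED, REML, unstructured covariance over the two visits; fixed effects group, time and group-by-time) that includes every patient with at least one observed value.
2. State that baseline comparisons of patients with healthy controls, including those in the second-level analyses, use all enrolled participants with a baseline value.
3. Keep the two-visit ANOVA as a complete-case sensitivity analysis.

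The cost is one paragraph and another procedure in the same software. No new data are needed, and the loss of precision is slight (0.322 against 0.313 in the example). The text should say that the model relies on missingness at random and does not correct dropout caused by worsening during the study.
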